### **Sample Size**

Below we give sample size calculations based on the gait outcome measures (six-minute walk test (6MWT), self-selected walking speed (SSWS) and fastest comfortable walking speed (FCWS)), as well as the expected changes in brain activations:

The sample size required per group is computed using the following formula:  $N$  (per group) =  $2 * ( (z(1-\alpha/2) + z(\beta)) * \sigma / d )^2$ , where  $d$  is the expected difference in outcome value, post- vs. pre-training;  $\sigma$  is the estimated standard deviation;  $\alpha$  is the alpha error we would like to control; and  $\beta$  is the statistical power. Here we set a statistical goal of 80% power ( $\beta = 0.80$ ,  $z(\beta) = 0.84$ ) and  $\alpha$  level 0.05 ( $z(1 - \alpha/2) = 1.96$ ).

Based on a recent study of locomotor rehabilitation in chronic stroke (Bowden et al., 2013), we expect: a difference in 6MWT of 154.3 +/- 171.1 meters; a difference in SSWS of 0.21 +/- 0.13 m/s; and a difference in FCWS of 0.18 +/- 0.15 m/s. These give sample size estimates of 20, 6 and 11 subjects, respectively. This sample-size estimate is conservative, using a two-tailed test when in fact we expect to test explicitly for an

increase (one-tailed test). For a one-tailed distribution (using  $z(1 - \alpha) = 1.65$ ), sample size estimates are 16, 5 and 9 subjects.

For fMRI signal changes at the single voxel level, we expect to achieve statistical power of 80% with a significance cutoff of alpha = 0.05 using a sample size of 12 subjects, as reported in literature (Desmond and Glover, 2002).

The maximum of all sample size estimates for two-tailed tests is 20 subjects. However, the outlier is the 6MWT; without this, the maximum would be 12 subjects. Balancing the practical (budgetary, time) need for a small sample with the need to capture as many metrics as possible, **we choose a sample size of 16**. This sample size just captures the expected change in 6MWT (in a one-tailed test) and is well above the necessary sample size for other outcomes. Based on previous experience, we estimate a 20% dropout rate (due to patients not being able to complete all sessions, or not coming back for post training evaluation). We therefore propose to enroll 20 patients per group (robotic, aerobic), for a total of 40 patients.

Up to 20 healthy controls will be enrolled to form a normal data set of similar size to each patient group.

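### The 6MWT gain that sets 16 per group is out of scale with the walking-speed gains beside it and unexplained; even as printed, it gives 16 per group about 69% two-sided power

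*Combined protocol and SAP*

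**What the plan says.** The Sample Size section draws three expected gains and SDs from one cited study of locomotor rehabilitation in chronic stroke: "a difference in 6MWT of 154.3 +/- 171.1 meters; a difference in SSWS of 0.21 +/- 0.13 m/s" and "a difference in FCWS of 0.18 +/- 0.15 m/s". It puts them into a two-group formula: "Here we set a statistical goal of 80% power", with alpha 0.05. For the two-tailed test it reports: "These give sample size estimates of 20, 6 and 11 subjects, respectively". For the one-tailed test, "sample size estimates are 16, 5 and 9 subjects".

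The section calls the 6MWT the outlier because of its N, notes that 12 would be the maximum without it, and settles on 16 per group. The stated ground is that "This sample size just captures the expected change in 6MWT (in a one-tailed test". A 20% dropout allowance then gives 20 enrolled per group.

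Under Subject Assessments, the 6MWT is distance walked in six minutes, with stops and rests permitted. SSWS and FCWS are speeds over 5 m. The Behavioral Data analysis plans repeated-measures ANOVA over time and a multivariate ANOVA with time and group as factors. It names no directional test.

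**The concern.** Distance in six minutes is average speed times 360 s, so the three rows can be put on one scale. On that scale the 6MWT gain is more than twice either walking-speed gain, and its SD is more than three times either speed SD, although all come from the same study. The plan does not comment on this and gives no baseline values that would account for it.

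The row matters because it is the only one that needs more than 12 per group, and the choice of 16 is worded as just enough for it. If its mean or SD is not what it is labelled as, the stated power for the first-named primary measure has no firm basis.

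**Working it through.** **Inputs.** From Sample Size: 6MWT 154.3 m, SD 171.1 m; SSWS 0.21, SD 0.13 m/s; FCWS 0.18, SD 0.15 m/s; z values 1.96 (two-tailed), 1.65 (one-tailed) and 0.84 (power). From Subject Assessments: test duration six minutes = 360 s.

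**1. Reproduce the plan's figures.** N per group = 2 x ((z_alpha + z_power) x SD / d)^2.

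- 6MWT, two-tailed: 2 x (2.80 x 171.1/154.3)^2 = 19.28, so 20. One-tailed: 2 x (2.49 x 171.1/154.3)^2 = 15.25, so 16.
- SSWS: 6.01 and 4.75 (stated 6 and 5). FCWS: 10.89 and 8.61 (stated 11 and 9).
- Dropout: 16/0.8 = 20.

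The plan's arithmetic reproduces. The question is about an input.

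**2. Put the rows on one scale.**

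- Mean: 154.3/360 = 0.429 m/s. Against SSWS, 0.429/0.21 = 2.04; against FCWS, 0.429/0.18 = 2.38.
- SD: 171.1/360 = 0.475 m/s. Against SSWS, 0.475/0.13 = 3.66; against FCWS, 0.475/0.15 = 3.17.
- Mean/SD: 6MWT 0.90, SSWS 1.62, FCWS 1.20.

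**3. What the printed means require.** Assume that mean six-minute speed after training does not exceed mean FCWS after training. Then baseline six-minute speed + 0.429 is at most baseline FCWS + 0.18. The baseline gap is therefore at least 0.429 - 0.18 = 0.249 m/s, or 154.3 - (0.18 x 360) = 154.3 - 64.8 = 89.5 m over the test.

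**4. Effect on N if the row is wrong.** The replacement values are assumptions: the speed rows converted to metres (0.21 x 360 = 75.6; 0.18 x 360 = 64.8; 0.13 x 360 = 46.8; 0.15 x 360 = 54.0).

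| Assumption | Mean, SD (m) | Two-sided N per group | 16 per group |
|---|---|---|---|
| Mean and SD share one scale error | ratio stays 0.90 | 19.3 | as in step 5 |
| Both move to the speed scale | 75.6, 46.8 or 64.8, 54.0 | 6.0 or 10.9 | ample |
| Mean falls, SD stays | 75.6, 171.1 or 64.8, 171.1 | 80.3 or 109.3 | 23% or 18% power |

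**5. Power at 16 per group with the printed inputs.** Noncentral t, 30 degrees of freedom, noncentrality 0.902 x sqrt(16/2) = 2.55: 69.4% two-sided, 80.2% one-tailed. The normal approximation, on which the plan's formula rests, gives 72.3% and 81.7%.

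**The case against.** The strongest reply is that nothing here is shown to be wrong. The plan's formula and inputs give its stated N. The tests measure different things: the 6MWT includes stops and slowing, so distance can rise through fewer rests or better endurance without an equal rise in speed over 5 m. A baseline gap of 0.25 m/s is not excluded by anything in the documents, and the cited study is not available here. N depends only on mean/SD, and on that ratio the questioned row is already the most demanding of the three. If it were deleted, 16 would still exceed every other stated requirement. The plan also says openly that the two-tailed 6MWT requirement is 20, and that 16 suffices only one-tailed.

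Most of this stands. A reader might infer that the plan's figures contradict each other. They do not, because rests are allowed and no baseline values are given. A reader might also infer that the trial really needs 80 to 110 per group. That holds only if the mean is replaced and the SD kept, yet the SD is further off the speed scale than the mean.

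Two things remain unanswered. The row on which 16 rests is out of scale with its neighbours, and the plan offers no explanation. And giving 20 as the two-tailed requirement does not tell the reader what power 16 has in the tests planned. The ANOVA tests are non-directional, although the Sample Size section says a one-tailed test is expected. Two-sided power would reach about 81% (normal approximation) only if all 20 enrolled per group completed, against the plan's own 20% dropout estimate.

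**Conclusion.** The concern holds as an unexplained scale mismatch in the input that drives the sample size. The 6MWT mean is 2.0 to 2.4 times the walking-speed gains and its SD is 3.2 to 3.7 times theirs. The baseline gap of at least 0.25 m/s rests on the assumption that six-minute speed after training stays at or below FCWS. The documents do not establish that the row is in the wrong unit, or is a level rather than a change; those are things to check. The direction of any effect on N is unknown.

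A separate shortfall does not depend on that check. Taking the printed mean and SD at face value as the between-group difference and its SD, 16 per group has about 69% power two-sided and reaches 80% only one-tailed.

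**What to change.** Check the 6MWT mean and SD against the cited study, both for unit and for change versus level. Correct them, or add a sentence justifying them, for example with the baseline six-minute and FCWS values. Then state the 6MWT power at 16 per group for the two-sided test that will be run; this is about 69% if the printed figures stand. If the row cannot be confirmed, delete the statement that 16 just captures the 6MWT change.

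Do not re-base the size on SSWS and FCWS as reassurance. The section defines d as a post- versus pre-training change and then uses it in a two-group formula, so those rows say no more about the between-group difference than the 6MWT row does.

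The cost is one source check, a few revised sentences and a less favourable stated power for the 6MWT. Enrolment stays at 20 per group.

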## Potential Risks and Benefits

### *Cycling*

Recumbent cycling at moderate intensity is widely considered a safe activity. Nevertheless, common risks associated with exercise may also occur in this study. These risks include muscle soreness, joint soreness, a feeling of exertion, and being out-of-breath. Robotic control of the cycle means that limbs may be driven through passive movements, and may be driven opposite to the forces generated by the user, which may increase muscle soreness. As with any device, there is a slight risk of malfunction; the cycle is equipped with emergency stops on the handles that suspend operation of the motor in this event.

### *EMG (electromyography):*

EMG is a diagnostic tool that evaluates muscle or nerve problems. It uses surface electrodes to assess the activity of muscles and the ability of motor neurons to control the muscular system. Risks associated with this procedure are minor and may include skin irritation and general soreness in the areas being tested. This may last for a few days and can be relieved with an over-the-counter pain reliever.

***Heart Rate Monitoring:***

A standard heart rate monitor will be strapped around each subject's chest. Risks associated with this measurement are minor, and include discomfort due to the strap and monitor module.

***Disease Transmission:***

Because the same rehabilitation cycle equipment will be used by multiple subjects, there is potential for disease transmission. This risk is reduced to an extremely small level by two mechanisms. Subjects reporting treatment for infectious disease will not be allowed to participate. Secondly, equipment surfaces with which subjects come in contact will be disinfected following each subject's use of the equipment.

***Functional MRI:***

MRI, a Class II device, is recognized as a Non-Significant Risk (NSR) device by the FDA. All the systems, features, and accessories that will be used in the scanning of subjects under this protocol will be operating outside the limits identified by the FDA as "Criteria for Significant Risk Investigations."

Within this context, there are still several potential hazards associated with a typical MRI scan. Subjects who will undergo an fMRI scan will be screened for MRI eligibility using the UW Department of Radiology's standard clinical MRI screening form, once during the phone screening and again immediately before each fMRI scan. Subjects will be excluded as necessary to minimize risk associated with possible MRI hazards including the following:

***Magnets and Metals:***

MRI systems are magnetic. They can attract metal objects. Metal in the body, such as pacemakers or metal fragments in the eye, can be moved and metal in the room can fly into the machine.

***Pregnancy:***

While there are no known adverse effects of magnetic fields on fetuses, there is no medical benefit provided by the studies done under this protocol. To be cautious, women who self-report that they may be pregnant or plan to become pregnant during the study period will be excluded from the study.

***Claustrophobia:***

The tube in the MR system where the subject will lie is small and some people react poorly to being in small places. Those who may react poorly will be excluded from the study.

***MRI:***

Aside from the standard risks associated with persons with certain metallic implants discussed above, no known risks of MRI exist. We know of no risks or adverse effects from the magnetic fields or radio waves used in the standard MRI pulse sequences. A small increase in risk may be associated with rapid gradient waveform switching times associated with fast MR imaging. In certain situations, the rapid switching of gradient waveforms has caused peripheral nerve stimulation in subjects. Significant nerve stimulation, however, has not occurred as long as the imaging system has been programmed to stay within certain limitations of gradient strength and switching time ( $\text{dB}/\text{dt}$ ). There is no reason to believe that risks may be different for the stroke patients to be recruited in this study. The MR scanners currently being used at the UW stay within these guidelines, and any additional pulse sequences which we program in our laboratory will be designed to stay within the current guidelines for  $\text{dB}/\text{dt}$  established by the FDA.

**Minimizing risks:**

Subjects are under supervision at all times during the experiments and will easily be able to communicate any discomfort. Equipment will be disinfected after every subject. The robotic cycle will be equipped with emergency-stop switches on the handle grips, which will disable the motor's power amplifier when released, bringing the machine to a stop.

To minimize risks in moving around the buildings, participants will be allowed to use any mobility aids (canes, walkers, wheelchairs, etc.) anytime they are standing or walking. Participants will be helped into and out of the seat on the robotic cycle by the project staff. For moving throughout the building, elevators and ramps are available. The exercise itself is a recumbent (seated) cycling exercise; the cycle will be equipped with a seatbelt that will be kept fastened during testing and training.

**Medical emergencies:**

We have an MD on call, [name], who will be available to respond and attend to any medical emergency during the course of a study session. In addition, we will contact 911 in the event of an emergency.

**Emotional Health of Subjects**

The CESD-R Assessment used in this study asks about symptoms of emotional distress such as depression. We will evaluate the results of this assessment on the same day it is taken. Written answers from subjects will be entered by an experimenter into the anonymous online version at <http://cesd-r.com>. The result reported by the system will be used to determine the subject's status relative to indicators of a major depressive episode (according to the criteria at <http://cesd-r.com/cesdr/> ). If major depressive episode is indicated as "possible," "probable," or "meets criteria," we will follow-up with the following actions:

- We will inform the subject that the assessment shows that (s)he may be having an episode of major depression, along with the severity/certainty rating reported by the CESD-R criteria.
- We will inform the subject that if (s)he is experiencing emotional distress, (s)he should contact his/her physician or other health care provider, such as a mental health professional.
- We will call 911 if the subject appears to be in immediate danger of harming himself/herself.
- We will give the subject the option of withdrawing from the study if (s)he desires.

No action will be taken if the CESD-R result indicates "subthreshold symptoms" or "no clinical significance."

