**Timeline:**

- **Timepoint 1 Visit** – will include baseline behavioral assessments, gait tests,

written questionnaires, and fMRI scan

- Training session #1 : [this could occur on the same day as the first behavioral and fMRI sessions]
- Visit 2 – training session #2
- Visit 3 – training session #3
- Visit 4 – training session #4
- Visit 5 – training session #5
- Visit 6 – training session #6
- Visit 7 – training session #7
- Visit 8 – training session #8
- Visit 9 – training session #9
- Visit 10 – training session #10
- Visit 11 – training session #11
- Visit 12 – training session #12
- **Timepoint 2 Visit** – will include endpoint behavioral assessments, gait tests, written questionnaires, and fMRI scan 2 at the end of the intervention . This visit could occur on the same day as the final intervention, or the next day or two per subject and experimenter convenience.–

Each behavioral session will take roughly 1 hour. Each intervention session will take about 1 hour. Each fMRI scan session will take 2 hours. The behavioral and fMRI sessions will take place at WIMR; the training sessions will take place at the UW-Madison Mechanical Engineering Building. We will arrange and pay for transportation between sites as needed.

Evidence suggests that targeted lower limb cycle training can improve walking distance and speed in stroke patients. Some example studies used a program of 10-15 training sessions over 2-3 weeks (Brown et al., 2005; Katz-Leurer et al., 2006), and 12 sessions over 4 weeks have been used in robotic gait training (Krishnan et al., 2013). This basis suggests that the intended duration and intensity of training (12 sessions of 30 minutes over 4 weeks) will be sufficient to demonstrate improvements in gait and motor function if they occur. However, this protocol is a target, which may be adjusted for individual patients as necessary to accommodate schedules and other needs. In such cases, the goal will be to keep the total number of training sessions constant for all patients. However, if interim results [after 6-10 patients] suggest that 12 sessions is not sufficient, then the study team will make provisions to increase the number of study sessions. Finally, if it appears that the subject will take more than 15 sessions to complete the study, then subject participation in the study will end.

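### CESD-R forms need only be scored on the same day, so the check for immediate danger may come after the subject has left; scoring before departure is a cheap, minor safety improvement

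*Combined protocol and SAP*

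**What the plan says.** The section Emotional Health of Subjects sets one time limit: "We will evaluate the results of this assessment on the same day it is taken". Subjects answer on paper, and an experimenter then enters the answers into an online scoring tool. If the tool places the subject in any of the three categories that suggest a major depressive episode, four actions follow. The subject is told the result, is advised to contact a physician or other provider if distressed, and is offered withdrawal. The fourth is an emergency step: "We will call 911 if the subject appears to be in immediate danger of harming himself/herself". None of the four carries a time or a mode of contact.

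Two nearby sections describe cover while the subject is on site. Under Minimizing risks, "Subjects are under supervision at all times during the experiments". Under Medical emergencies, there is an on-call physician "who will be available to respond and attend to any medical emergency during the course of a study session".

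On the visit schedule, the closing visit "will include endpoint behavioral assessments, gait tests", and the opening visit has the matching baseline set. Under Timeline, "Each behavioral session will take roughly 1 hour", a scan session takes 2 hours and a training session about 1 hour. The first training session may share a day with the baseline assessments and scan. The summary of study visits calls the schedule representative and allows events to be split across visits.

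**The concern.** A same-day rule is not a before-departure rule. Someone who completes the form at the end of a morning session and leaves can be scored that evening in full compliance. If the result is positive, staff must then judge whether a person they can no longer see is in immediate danger. Supervision and physician cover, as worded, belong to the experiments and the session, and both would be over.

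There is a second, smaller consequence. The withdrawal offer is of most use before further procedures. At Timepoint 1 a late score could bring it only after the scan and the first training session.

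What is at stake is the safety of a subject with a positive screen, not the validity of the trial's results.

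**Working it through.** The plan gives no figure to reproduce. The check sets the sections side by side and asks what they allow.

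**1. When the score exists.** It exists after data entry, not when the subject puts the pen down. The four actions are triggered by the score, so they cannot start earlier on that ground.

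**2. Whether any other section requires scoring before departure.** None does. Minimizing risks and Medical emergencies describe cover during the experiments and sessions; neither mentions when the CESD-R is scored.

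**3. Which actions survive departure.**

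| Action | Possible by phone? |
|---|---|
| Tell the subject the result | Yes |
| Advise contact with a provider | Yes |
| Offer withdrawal | Yes, but perhaps after same-day procedures |
| Call 911 on apparent immediate danger | Harder: it rests on how the subject appears |

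**4. Whether the visit has room for scoring.** Session lengths are from Timeline.
- Behavioral session alone: about 1 h.
- Behavioral plus scan: 1 + 2 = 3 h.
- Timepoint 1 with the first training session on the same day: 1 + 2 + 1 = 4 h, plus transport between sites.

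If the form is given last, the time left on site is about zero. If it is given first, the time left is just under 1, 3 or 4 h respectively. Entry of the 20 items is assumed to take 5 to 10 minutes; the documents give no figure. Scoring therefore fits every layout if the form comes early. It does not fit, without extending the visit, if the form is the last item before departure.

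**5. How many forms are planned.** Patients complete the measures at two timepoints and matched controls once (Behavioral Assessment; Non-Stroke Group 1). With 40 patients and up to 20 matched controls, the number is 40 × 2 + 20 = 100 at most, before dropout. Pilot subjects, who complete only a subset of measures, and any replaced dropouts are not counted. The share that would screen positive or be scored late cannot be derived.

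**The case against.** The strongest reply is that the gap is hypothetical. The plan already has a dedicated pathway with same-day evaluation, a defined threshold, notification, referral advice, an emergency step and optional withdrawal. Staff can notice visible distress during the visit whatever the score, and nothing stops them scoring on the spot. This stands, and it is why the point is minor. It does not remove the fact that late scoring complies and weakens one of the four steps.

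Three stronger readings are tempting, and the documents do not support them.

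- A reader might infer that forms will be scored after departure, or that the protocol promises follow-up face to face. It says neither. No mode of contact is stated, and three of the four actions work by phone.
- A reader might infer that leaving the site ends all emergency response. The on-call physician's cover is tied to the session, but the separate commitment that "we will contact 911 in the event of an emergency" is not expressly so limited.
- A reader might infer that "No action will be taken if the CESD-R result indicates" a lower category leaves a visibly distressed subject without help. That sentence governs the response to a score, and the general emergency commitment names no category.

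The two-week review of behavioral measures in the Data and Safety Monitoring Plan does not add to the case either. It is a general rule, and the same-day rule for this form is specific and stricter.

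**Conclusion.** The point holds as a minor participant-safety improvement. The rule as written permits scoring after the subject has left. In that event the check for immediate danger must be made at a distance, and at Timepoint 1 the offer of withdrawal may follow the scan and first training session. This is an unspecified step, not a contradiction in the plan or evidence of an unsafe practice. The number of subjects affected is unknown.

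Confidence is medium. The text is clear, but the importance of the gap depends on when staff actually score the form, which the documents do not say. The judgment that scoring fits the visit rests on the assumed 5 to 10 minutes of entry time.

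**What to change.** In Emotional Health of Subjects, replace the same-day limit with a requirement that results be evaluated before the subject leaves the visit at which the form is taken. Give the form early enough in the visit to allow this. Add a fallback: if scoring cannot be completed, for example because the scoring website is unavailable, the subject is phoned the same day.

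The cost is an assumed 5 to 10 minutes of data entry moved into the visit, and a short IRB amendment. No extra visit, instrument or staff role is needed. In a combined visit the entry can be done during the scan session if a staff member is free, but the withdrawal offer then still follows the scan; entry before the scan avoids that. In a separate behavioral session of about 1 hour, an early form lets the entry run alongside the other tests; otherwise the session is extended by those minutes.
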